#### *Protections Against Potential Risks*

We have strict data security and confidentiality procedures in place as described below. All research staff are required to sign a confidentiality pledge and to complete human subject's research training. Moreover, the data will be stored on a firewall protected, restricted access server that is only accessible to select Health Lab researchers. Additionally, the survey data will be collected through University of Chicago's REDCap system which meets all HIPAA requirements for data security. For the potential risks relating to vitamin D toxicity and insufficiency, we think these are very low but will inform participants of them prior to their participation in the study.

Furthermore, participants will be given a contact number and email address for study staff and encouraged to monitor for and report any possible signs of vitamin D toxicity, and to report any COVID-19 symptoms or positive tests. Participants will also be given instructions for any home testing-related risks such as bruising or bleeding risk. Participants will be advised to seek medical care immediately for any problem they view as urgent and the PI will be informed within 24 hours. In the event of an unanticipated problem, study staff will inform the PI within 24 hours, and document study protocol number, participant's initials, date of event, and description of event. Study staff will then formally submit an "Unanticipated Problem Event Form" to the UChicago Biological Sciences Division IRB within 5 days.

#### *Potential Benefits*

We believe this research will have large benefits to society. One of the key challenges in addressing COVID-19 is the lack of rigorous RCT's on potential pharmacologic solutions to pandemic. Thus, this research has the potential to contribute to the ongoing solutions being tested to alleviate the health impacts of COVID19 in our society. Furthermore, as the world awaits a potential vaccine, many policymakers and communities will be interested in understanding how low-cost preventative measures can help people at risk of contracting COVID-19.

#### **XI. Monitoring of safety:**

The current study represents a single-site clinical trial in which the risks inherent to the intervention are of minimal risk to participants given the long-standing use of vitamin D supplementation with few adverse events. The protocol's exclusion criteria and monitoring plan limit the likelihood that subjects will develop a severe medical condition during the course of this study. Commensurate with these risks, the PI [name], with support from the Clinical Advisory Committee and co-investigator [name], will incorporate this study into an already established formal Data and Safety Monitoring Board (DSMB). Given the low reported COVID rates and low reported rates of potential side effects from vitamin D treatment, we will utilize the DSMB we have already convened for our NIH Vitamin D study (IRB20-1302), which currently meet quarterly. This independent DSMB has been set up and is comprised of three experts, a Chair and two members, who have been providing regular oversight for that study. These individuals are senior faculty members and hold expertise in clinical trial oversight and design, biostatistics, endocrinology, pulmonology and critical care medicine. Further, these individuals are the same experts we identified in the DSMB Charter below.

To date, the NIH DSMB has met twice, once in June 2021 and again in August 2021, and has identified no patient safety concerned (note the NIH study includes the same doses as Vitamin D as this study, as well as one arm with a higher dose of 10,000 IU per day). We plan to bring more data analysis from this study to next quarterly joint-DSMB In December 2021. We believe this is justified given the absence of any evidence of adverse outcomes in this study to date. In addition, due to lower than anticipated enrollment and the studies being so complementary, we plan to eventually combine the two studies samples at a later date and will submit additional amendments to reflect this change. In the meantime, introducing this study to the existing DSMB is one of the first steps of merging these studies.

The protocol's safety and monitoring guidelines as described below have been created in collaboration with the already-identified members of the Clinical Advisory Committee, a committee of interdisciplinary clinicians who will provide the PI clinical support and guidance. The protocol will be overseen by the DSMB which will provide continued guidance on administration of the study protocol and management of any adverse events. The DSMB will work closely with the PI, co-investigators, and Clinical Advisory Committee, monitoring the intervention on an ongoing basis and meeting quarterly to review intervention data and provide recommendations as needed for modifying the intervention.

#### *Ensuring subject safety*

The proposed study will be supervised by PI and the Clinical Advisory Committee, with oversight by the University of Chicago Biological Sciences Division Institutional Review Board (UCM BSD IRB). All subjects will sign an electronic consent. Additional safety precautions include: 1) exclusion of individuals for whom higher dose vitamin D supplementation is more likely to be unsafe, 2) written materials on possible side effects of vitamin D supplementation provided at consent (i.e., risk of falls, symptoms of hypercalcemia), 3) participants will be advised to report adverse events (email and study phone number provided), 4) independent testing of vitamin D supplements to ensure accurate potency, 5) participation in the study is entirely online and remote, mitigating any additional spread of COVID-19 and 6) well-trained research staff.

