In addition to these questions, we have added some questions on the baseline and follow-up surveys that evaluate sleep habits as well as additional possible risk factors for COVID-19 outcomes. These risk factors—hypertension, diabetes, and mood—are shown to have possible linkages to vitamin D levels. These factors are receiving increased attention in the context of COVID-19 risk and its relationship to low vitamin D levels. While available evidence suggests there is a link between hypertension/cardiovascular disease, diabetes and metabolism, depression/anxiety, and vitamin D levels, to-date no causal relationship has been established. This is supported by both evidence as recently as this year, as well as earlier studies. Questions about hypertension and diabetes are of our own construction, and questions about depression and anxiety come from validated instruments, the GAD-2 and the PHQ-2. We hope to shed light on the relationship between our outcomes of interest, vitamin D, and these risk factors by asking subjects, both already enrolled and new, about these factors.

Our data management plan will specify procedures to collect, organize, handle, clean, analyze, describe, preserve, destroy, report and share data. We will review self-reported survey data regularly to prevent and monitor missing data. We will record and report all known reasons for study dropout and missing data. For our primary outcome of COVID-19 infection as measured by patient report of clinically confirmed COVID-19 (or viral PCR if available) and COVID-19 seroconversion tests that data collection, hazard models will be used to assess the effect of vitamin D dosing on the outcome. We will first develop hazard ratios for between-group analyses on the primary outcome using log-rank tests, and then Cox proportional hazard models with covariates including vitamin D dose, age, gender, race, ethnicity, sun exposure, exposure of cohabitants,

employment status, and geographic location. Secondary study outcomes of hospitalization, ICU use, mechanical ventilation use and death will be analyzed with longitudinal mixed models with these covariates.

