For 20% of the subjects, blood samples to test for Vitamin D levels and COVID-19 antibodies will be obtained at the beginning of the study by two different vendors: Everlywell and Rush Hospital. Originally, the entire study sample was offered antibody testing at the end of the study. We paused end of study antibody testing in early 2024 due to low return rate and now wish to permanently discontinue it. Over the course of this three year study, it is likely that most participants have COVID-19 antibodies, therefore testing is no longer scientifically valuable. The vitamin D test is a standard commercially available vitamin D home test and provides a number level measured in ng/ml. We currently plan to source this from Everlywell (<https://www.everlywell.com>). We will register vitamin D test kits with Everlywell on each subject's behalf, using subject's name and the test kit ID. Our current plan for the antibody test is to use the 'Rush Covid-19 Multi-analyte Serological Assay', which evaluates an immune response to four SARS-CoV-2 antigens, including the spike S1, nucleocapsid, matrix, and envelope glycoproteins in individuals convalescing from Covid-19. This assay has been developed by [name] at Rush and is built on the Luminex immunobead platform and was specifically engineered to provide greater confidence in diagnostic results through the use of an algorithm integrating results from the four independent assay findings and requires no less than two analytical findings to deliver a diagnostic result to significantly reduce the rate of 'False Negative' misclassifications. The analytical performance characteristics of the Rush Covid-19 Multianalyte Serological Assay have been calculated to be 100% sensitivity and 99.6% specificity with a 99.62% accuracy when evaluated against 44 cases with clinically-diagnosed Covid-19 within a window of 8 and 30 days from testing and 998 cases of pre-Covid-19 era (i.e. prior to 6/2019) specimens. This assay will be performed in [name] Development Facility, which falls under Rush Pathology's CLIA license. Both the Vitamin D and antibody blood tests will be self-administered, at-home, with no in-person contact, and will be mailed back to the vendors.

Survey data will be collected quarterly by the study team via a HIPAA-secure Redcap survey. Data will be stored on encrypted-password protected computers, locked filing cabinets, and secured encrypted drives in these offices.

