## **VI. Special precautions, including dose modifications**

We will not make modifications of the vitamin D dose based on the study design. As described in Section XI, "Monitoring Subject Safety", subjects will be advised to cease vitamin D supplementation if they experience adverse effects commensurate with hypercalcemia. Subjects will be asked to discontinue taking any non-doctor recommended supplements containing more than 1,000 IU of vitamin D when they begin taking study-provided supplements.

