As noted, we plan to recruit 20% (200 participants) of the eligible participants at the beginning of the study to receive and complete a self-guided, at-home vitamin D level and a COVID-19 anti-body test at their places of residence. At the end of the study, all study participants were to be offered an at-home COVID-19 antibody test kits. Please note that these tests were halted in early 2024. Participants will have the option to opt in or out of these tests on the study consent form. Participants who opt out of the at-home antibody test will still be able to participate in the study and receive Vitamin D supplements.

Participants will have the option to receive their vitamin D results and their antibody test results at the end of the study. If positive, communication of the antibody results will clearly indicate that there is evidence of past exposure to SARS Cov2 virus but that it is not known whether such indication is related to the presence or absence of immunity to future infections. To ensure only secure release of information, request for release of information will only be honored when communicated by email or text from the email address or cell phone number used to register the participant, and will be provided by mail only to the address registered by that individual upon enrollment.

During the 12-month implementation period, we will ask participants to complete online follow-up surveys every 3 months. The follow-up surveys at months 3, 6, and 9 will ask the participant whether they have had a

confirmed diagnosis of COVID-19, and the date if so, ask about rates of study medication adherence, and assess for changes in the intake questions about use of other supplements, sun exposure, diet, exercise, and COVID-19 exposures. If the patient is reported to have had COVID-19, we ask about severity, including hospitalization and duration, type of COVID-19 testing used, and need for mechanical ventilation and duration, and COVID-19 symptom severity using the BEAT-19 adapted to reflect the worst symptomology during their period of active COVID-19.

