## **X. Potential risks and benefits to subjects:**

*There are four minimal risks associated with the baseline survey and overall study participation.*

Confidentiality risk: There is a small chance that someone could find out that a subject is participating in this study or access the study data. However, we will take every precaution to protect subject privacy. In addition to using the Health Labs limiting data access to specified research staff, each person on the research team will be trained in human subject's protections and HIPAA policies and best practices. Additionally, we will minimize the risk of exposure or accidental disclosure to the fullest extent possible by maintaining all research data only on secure, password and firewall protected network computer accounts, limiting access to those data files to members of the research team, and only communicating data findings in the aggregate form. All names and other protected health information will be deleted from study records whenever possible. For example, in analytic datasets, participants will typically be identified by their unique study numbers.

Vitamin D toxicity risk: There is a very small chance that a participant could develop symptoms of vitamin D toxicity, including hypercalcemia, falls, hyperparathyroidism, or kidney stones. The health issues above are included in our exclusion criteria to further minimize this risk. Risk of toxicity could also be increased if patients take other vitamin D supplements, which they will be advised not to do. All patients will be informed about symptoms of vitamin D toxicity and advised to contact their physician if symptoms occur. The highest dose

administered as part of the study is considered by the National Academy of Medicine as low risk for the vast majority of the population without direct medical supervision,

Vitamin D insufficiency risk: There is a risk that some people in the 400 IU group may consume less than the daily RDA (600 IU) once diet (~200-300 IU/day) and the supplement are accounted for, but this risk is very low and reduced compared to not taking any vitamin D supplement. Persons whose doctors have advised higher doses will be excluded from the study.

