##### *Monitoring Frequency*

The DSMB will meet to review initial laboratory values and quarterly thereafter to review the overall protocol administration, review adverse events, and trends in laboratory values for determination of safe progression of the study. DSMB members will schedule additional meetings as needed to review adverse events.

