#### **XVII. Notification of primary physician:**

Subjects' primary care physicians will not be notified of subjects' involvement in the proposed research. One exception to this is if a subject is counseled to seek care from their primary care physician due to an abnormal laboratory result or symptom as described above.

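### As described, toxicity events become known only if participants report them, the DSMB's laboratory trends cannot be produced, and the SAP has no by-arm harms analysis

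*Protocol*

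**What the plan says.** **Reporting routes.** Among the precautions in Protocol Section XI (Ensuring subject safety), "participants will be advised to report adverse events (email and study phone number provided". Section X (Protections Against Potential Risks) and Section XIV likewise ask participants to watch for toxicity signs and tell staff. Both add that urgent problems should be taken straight to medical care and that the PI will hear within 24 hours; neither says how. On toxicity, Section X states: "All patients will be informed about symptoms of vitamin D toxicity and advised to contact their physician if symptoms occur". Section XIX relies on the participant to disclose a pregnancy. Section VI says "subjects will be advised to cease vitamin D supplementation if they experience adverse effects commensurate with hypercalcemia" and points to Section XI for details.

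**Surveys.** Section VIII itemises months 3, 6 and 9: confirmed COVID-19 and its date, adherence, and a check to "assess for changes in the intake questions about use of other supplements, sun exposure, diet, exercise, and COVID-19 exposures". Severity and hospitalization are asked of those who report COVID-19. Section III adds sleep, hypertension, diabetes and mood, and promises: "We will record and report all known reasons for study dropout and missing data".

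**Laboratory data.** The DSMB charter (Monitoring Frequency) has the board look at initial laboratory values and then, each quarter, "review adverse events, and trends in laboratory values for determination of safe progression of the study". Section V says that for 20% of subjects "blood samples to test for Vitamin D levels and COVID-19 antibodies will be obtained at the beginning of the study". The end-of-study antibody test has been discontinued.

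**SAP.** It covers time to COVID-19, subgroups, calendar-quarter effects, COVID-19 severity, proportional hazards, missing data and multiplicity.

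**The concern.** Section X names the toxicities of interest: hypercalcemia, falls, hyperparathyroidism and kidney stones. Participation is entirely remote and each bottle holds a 12-month supply, so no visit or refill contact is described at which staff would ask about them. If nobody asks, a low count cannot separate few events from few reports.

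This matters here for two reasons. First, Section XI defends the shared DSMB arrangement partly by the lack of adverse findings in this trial so far, and that evidence is only as good as the reporting behind it. Second, Section III says 4,000 IU/day was chosen so that the intervention could be rolled out widely without clinical supervision. Readers deciding on such use will want harms by arm, and the SAP does not plan to produce them.

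**Working it through.** No stated figure in the plan needs reproducing. The check is mainly textual.

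**1. Who starts each report?** Email or phone to the team (Sections X, XI, XIV): the participant. Pregnancy (Section XIX): the participant. Contact with their own physician (Section X): the participant, and Section XVII says physicians are not told of enrolment unless a subject is "counseled to seek care from their primary care physician due to an abnormal laboratory result or symptom as described above". Urgent problems (Sections X and XIV): the PI is to be informed, by an unstated route. PI to DSMB (charter, Adverse Event Management): this passes on only what the PI already knows.

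**2. Do the surveys ask?** The items listed in Sections III and VIII include none of the four toxicities named in Section X. Adherence and dropout reasons are partial signals. They may show who stopped, but not who had an event and carried on.

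**3. Can laboratory trends be reviewed?** Tests described: one vitamin D level and one antibody test, at baseline, in 20%. Calcium, creatinine and parathyroid hormone tests described: none. Scheduled post-baseline safety tests: zero. The consent text in Section XIII speaks loosely of testing at the beginning or end, but a single end value would still not give a quarterly trend. The abnormal laboratory result that Section XVII treats as already described has no such description.

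**4. Does the SAP analyse harms?** No adverse-event, toxicity or discontinuation comparison appears. Hospital admission and death appear only as COVID-19 severity.

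**5. What incomplete capture does to a comparison.** Let p1 and p0 be the true risks and c the share of events captured, taken as equal in both arms because dosing is blinded.
- Observed risk ratio = c·p1 / (c·p0) = p1/p0, unchanged.
- Observed risk difference = c·p1 − c·p0 = c·(p1 − p0), shrunk toward zero. At c = 0.5 it is halved.

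**6. Illustration for zero reports.** With n participants and no reports, the one-sided 95% upper bound on the reported risk is 1 − 0.05^(1/n). Dividing by c gives the bound on the true risk. Section VII puts half of 2,000, that is 1,000, on 4,000 IU/day; 500 is assumed because Section III reports low enrolment. All values of c are assumed.

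| Capture c | n = 1,000 | n = 500 |
|---|---|---|
| 100% | 0.30% | 0.60% |
| 80% | 0.37% | 0.75% |
| 50% | 0.60% | 1.19% |
| 25% | 1.20% | 2.39% |

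The documents give no capture rate. The 80% follow-up target in Section IV does not supply one, because it also counts people followed only until they report COVID-19. Zero reports is not a sensible scenario for falls, which happen regardless of treatment.

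**The case against.** The strongest reply is that much of this is argued from silence. Section VIII summarises the surveys rather than reproducing them, month 12 is not itemised, and Section XI mentions routine safety review. A reader might infer that the trial never asks about toxicity. The documents do not support that: a solicited question may exist in forms we cannot see. What stands is that the plan as written describes none.

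The 24-hour provision for urgent problems is a real counter-route, so care-seeking is not wholly cut off from the study. It covers only urgent problems, though, and its mechanism is missing.

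The charter wording may simply be out of date. Initial laboratory values do exist for the 20% subset, and a full-sample end-of-study antibody test was once planned. Even so, an antibody test is not a toxicity measure, and one end value is not a quarterly trend.

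The risk is low. The dose is the highest the IOM considered safe without supervision, people at risk are excluded, and the DSMB found no concern in two reviews of the sister trial, which included a 10,000 IU/day arm. A reader might infer that participants are in danger or that monitoring is unacceptable; nothing here shows that. Light monitoring is reasonable at this dose.

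Finally, the numerical bounds might be read as findings about this trial. They are not, because both the zero count and the capture rates are supposed.

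**Conclusion.** The concern holds for the plan as described. Toxicity events are collected from participants who choose to report them, the charter assigns a laboratory review that the data cannot support, and the SAP has no by-arm harms analysis. The last two findings stand whatever the survey forms contain; the first would fall if those forms already include toxicity items.

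The consequence is limited to what can be said about harm. Under-capture understates absolute risk and shrinks the risk difference in proportion to c. If capture is equal between arms, as blinding makes plausible, it does not distort the risk ratio, though it leaves fewer events to estimate it from. The primary efficacy analysis is not affected and no power claim is made. The tabulated bounds (0.30% to 1.20% for 1,000 participants) only show how the reading of a zero count depends on assumed capture.

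**What to change.** 1. **Surveys, while any remain.** Add short dated yes/no items on diagnosed hypercalcemia or its symptoms, kidney stone, hyperparathyroidism, fall and pregnancy. A yes alerts the PI and repeats the stop-and-contact advice, which should also be stated in Section XI. If such items already exist, describe them in the protocol.
2. **DSMB charter.** Replace the laboratory trends with by-arm counts of these items over surveys completed, seen by the DSMB only, so that the study team stays blinded as Section XXI intends.
3. **SAP, before unblinding.** Add a by-arm table of reported adverse events with n/N, and both the risk ratio and the risk difference with 95% CIs. Label events as solicited or volunteered. Note that incomplete capture shrinks the risk difference and that a low volunteered count is not evidence of safety.

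Timing decides how much applies. The SAP's last randomization quarter runs to April 2024, so 365 days of follow-up end by about April 2025. If follow-up has ended, do only item 3.

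The cost is a few survey items and one amendment, with no visits or blood tests; the table needs no new data. A few participants may stop tablets that were not the cause. Survey items will not detect asymptomatic hypercalcemia.
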